Dose evaluation will be guided by safety and PK profiles. Safety will be assessed by review of AEs, including DLTs; clinical laboratory tests, and vital signs. Anticancer activity will be evaluated using bone scan and computed tomography (CT) of the chest, abdomen, and pelvis, per Prostate Cancer Clinical Trials Working Group 3 (PCWG3).

The recommendations of the PCWG3 will be used to determine response ([Scher et al. 2016](#)). Tumor assessments will include ^{99m}Tc-methylene diphosphonate radionuclide bone scintigraphy and CT of the chest, abdomen, and pelvis within 28 days before the first dose of enzalutamide (for Dose-Determination Phase Segment 1) and/or CORT125281 (for Dose-Determination Phase Segment 2 and Expansion Phase) and at intervals of 8 weeks after the first dose of study treatment for the first 24 weeks. Thereafter, tumor assessments will occur at intervals of 12 weeks until disease progression. Objective responses will be confirmed no less than 4 weeks after the criteria for response are first met (if possible, 4–6 weeks). PSA, alkaline phosphatase (ALP), and lactic dehydrogenase (LDH) will be assessed at the Baseline/Screening Visit and Day 1 of each cycle. Results will be documented in the electronic case report form (eCRF). Tumor assessments will be documented until disease progression. Documentation of overall survival including subsequent therapies with duration and response will continue every 4 months until 2 years from the date that the last patient enrolls in the study or until all patients have completed follow-up for radiographic disease progression (whichever is later).

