4.1 Inclusion Criteria

Each patient must meet the following criteria to be enrolled in this study:

1. Able to understand the purpose and risks of the study; willing and able to adhere to scheduled visits, treatment plans, laboratory tests, and other study evaluations and procedures, and provide written informed consent.
2. Males ≥ 18 years of age at time of signing consent.
3. Histologically confirmed adenocarcinoma of the prostate with metastatic disease.
4. Dose-Determination Phase Segment 1 and Expansion Phase: Progressive disease as defined by PSA or imaging after most recent prior therapy. PSA ≥ 1 ng/mL, if a confirmed rise in PSA is the only indication of progression. Progression by PSA requires rising PSA over a previous reference value by at least 2 measurements obtained ≥ 1 week apart. PSA measurements can be collected during or after the most recent prior therapy.
5. Dose-Determination Phase Segment 2: Currently receiving enzalutamide with a rising PSA as follows:
 - a. Rising PSA: 25% increase over nadir and an absolute value of >1 ng/mL by at least 2 measurements obtained ≥ 1 week apart. PSA measurements can be collected during or after the most recent prior therapy.
 - b. Patients must have received enzalutamide for a minimum of 12 weeks and be on stable doses of enzalutamide ≥ 80 mg QD for at least 4 weeks prior to Cycle 1 Day 1.
 - Patients will continue enzalutamide without interruption during the Screening Period (no wash-out period).
 - This will be the enzalutamide starting dose for combination with CORT125281 beginning on Cycle 1 Day 1.
 - c. M0 disease is allowed.
6. Expansion Phase: Patients must have progressed while receiving an androgen-directed therapy as follows:
 - a. Abi-Resistant Cohort: Patients must have progressed during treatment with abiraterone.
 - b. ARant-Resistant Cohort: Patients must have progressed during treatment with enzalutamide or second-generation AR-blocking therapies. Patients progressing on enzalutamide immediately prior to enrolling in this study must be on stable doses of enzalutamide. These patients will continue enzalutamide without interruption during the Screening Period (no wash-out period required).
7. Baseline tumor assessment performed within 28 days prior to the first dose of study treatment (CORT125281 and/or on-study enzalutamide, whichever is earlier).

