9.1. Secondary Efficacy Endpoints

Objective Response Rate (ORR): Patient listings of tumor response outcomes (CR, PR, non-CR/non-progressive disease, stable disease, progressive disease, unevaluable, or not assessed) at study visits, as well as best overall response per RECIST v1.1, will be presented by treatment regimen dose group and overall for the ITT population. By-group summary tables will include distribution of response outcomes, best overall response derived over all visits, and point estimates with Clopper-Pearson² 95% CIs for ORR, defined as the proportion of patients with an objective tumor response (either PR or CR) in patients with measurable disease, including best radiographic response for soft tissue.

For supportive purposes, best overall response and point estimates with Clopper-Pearson 95% CIs for ORR will also be summarized using confirmed response.

PSA Levels: PSA levels recorded at each visit will be listed. Proportions of patients in the Safety population who experience a 50% or greater reduction in PSA levels at any visit since baseline will be reported with Clopper-Pearson 95% CIs by treatment group and overall. Mean reduction levels will be characterized via summary statistics. Median time from date of first dose of exicorilant to PSA progression (first occurrence of 50% or greater increase in PSA levels), along with 95% CIs will be estimated via Kaplan-Meier method, and also plotted graphically by treatment group. Patients who are alive and progression-free will be censored at the date of their-last PSA evaluation.

In dose escalation and expansion phases separately, best PSA response will be illustrated graphically via waterfall plots. For each patient, the maximum percent change in PSA levels since baseline will be depicted on the response axis, with vertical bars below the baseline representing decline in the blood-based marker.

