Symptomatic Skeletal Event (SSE): SSE is defined as symptomatic fracture, radiation or surgery to bone, or spinal cord compression. SSEs include only symptomatic events of clear clinical significance. Kaplan-Meier estimates of median time from date of first dose of exicorilant to the first occurrence of SSE and associated 95% CIs, will be computed by treatment regimen dose group and overall for the Safety population. Patients who are event-free will be censored at the date of their end of study/treatment + 30 days visit. Kaplan-Meier graph of the probability of the event will also be constructed by treatment group.

Radiographic progression-free survival (rPFS): For the Response-Evaluable population, rPFS will be determined from the first dose of study treatment (exicorilant and/or enzalutamide) to the date when the first site of disease is found to progress on CT, MRI, or radionucleotide bone scan per PCWG3, or death, whichever occurs first. Progression will be assessed by the Investigator using RECIST v1.1.

$$\text{rPFS (months)} = (\text{earliest date of progression, death, or censoring} - \text{date of first study treatment} + 1) / 30.4375$$

Patients who do not experience disease progression or death (due to any cause) will be right-censored at the time of the last tumor assessment date. Censoring date will be based on the date patient was last known to be alive and progression-free (i.e., last assessment date) or data analysis cutoff date, whichever occurs first. Censoring rules are summarized in [Table 3](#) below.

Table 3: Censoring Rules for the Primary Analysis of PFS

Censoring Categories	Date of Censoring
Patients who did not have baseline or postbaseline tumor assessments and did not die on or before the data cutoff date	Date of first study treatment

Patients who did not have disease progression as determined by the Investigator and did not die on or before the data cutoff date	Date of the last adequate tumor assessment on or before the data cutoff date
Patients who did not have disease progression as determined by the Investigator on or before initiation of subsequent anticancer therapy for prostate cancer and did not die on or before the data cutoff date	Date of the last adequate tumor assessment on or before initiation of subsequent anticancer therapy and on or before the data cutoff date

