Patients who had 2 or more consecutive missed scheduled tumor assessments immediately prior to disease progression	Date of the last adequate tumor assessment without evidence of disease progression before the 2 missed tumor assessments and on or before the data cutoff date
Patients who did not have disease progression as determined by the Investigator and died more than 119 days from most recent tumor assessment.	Date of the last adequate tumor assessment on or before the data cutoff date

Note: If a patient meets the criteria for more than 1 censoring rule, PFS will be censored at the earliest censoring date.

Kaplan-Meier curves will be plotted by treatment regimen dose groups, and the estimate of median rPFS time (months) with 95% CI will be ascertained. For each cohort, progression-free rate at 4, 6, and 12 months will also be summarized.

Duration of response (DOR): Duration of response will be defined for patients in the Response-Evaluable population as the time from the first occurrence of a documented objective tumor response of CR or PR to the time of radiographic progression (per Investigator using RECIST v1.1) or death from any cause on study, whichever occurs first. Patients who have not experienced disease progression or death will be censored at the time of the last tumor assessment date. Date of censoring will be determined according to same rules as described for rPFS endpoint.

$$\text{DOR (months)} = (\text{earliest date of progression, death, or censoring} - \text{date of first documented objective response} + 1) / 30.4375$$

Kaplan-Meier graph will be plotted by treatment group and estimates of median duration with 95% CIs will be obtained for each dose cohort and overall. Patients who do not achieve a tumor response of CR or PR, will be excluded from this analysis.

Clinical progression: For the Response-Evaluable population, clinical disease progression, defined as time from first dose of study treatment (exicorilant and/or enzalutamide) to date of treatment discontinuation due to disease progression, will be estimated via the Kaplan-Meier

method. Patients who are alive and progression-free will be censored at their end of study visit. Median time to progression and associated 95% CIs will be summarized, overall and by treatment group. Kaplan-Meier graph of the probability of the event will also be plotted by treatment group.

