Bone disease progression: For the Response-Evaluable population, bone disease progression, defined as time from first dose of study treatment (exicorilant and/or enzalutamide) to first confirmed appearance of at least 2 new bone metastatic lesions, will be estimated via the Kaplan-Meier method. Cases of equivocal progression will be confirmed by a repeat scan 8 weeks later. Patients who are alive and progression-free will be censored at their end of study visit. Median time to progression and associated 95% CIs will be summarized, overall and by treatment group. Kaplan-Meier graph of the probability of the event will also be plotted by treatment group.

Overall survival (OS): Overall survival will be calculated as the time from the first dose of study treatment (exicorilant and/or enzalutamide) to the date of death from any cause. Deaths that occur on or before the data cutoff date will be considered an event. If a patient has not died before the analysis cutoff date, OS will be censored at the date of last contact on or before the data cutoff date. The last contact date will be derived as follows:

Source Data Conditions	Source Data Conditions
Date of randomization	No condition
Last contact date/last date patient known to be alive from Long-Term Follow-Up eCRF	Use if patient status is reported to be alive Do not use if patient status is reported unknown
End of study	Not lost to follow up
Start/end dates of postbaseline antineoplastic therapy	Nonmissing medication/procedure term
Start/end dates from drug administration record	Nonmissing dose. Doses of 0 are allowed.
End of treatment date from the End of Treatment eCRF	No condition
Investigator overall tumor response assessment date	Evaluation is marked as done.
Laboratory/PK collection dates	Sample collection marked as done.
Vital signs date	At least 1 nonmissing parameter value
ECOG performance status date	Nonmissing ECOG performance status
Start/end dates of adverse events	Nonmissing verbatim term
Physical examination	Evaluation is marked as done.
ECG	Evaluation is marked as done.

The OS in months is defined as follows:

$$\text{OS (months)} = (\text{earliest date of death or censoring} - \text{date of first study treatment} + 1) / 30.4375$$

Median, 25th and 75th percentiles of OS, in months, with 95% CIs will be summarized and plotted graphically by treatment arm and overall using the Kaplan-Meier method.

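### Bone and clinical progression are censored at an undefined end-of-study visit, which overstates both times if it means end of follow-up; separately, PSA progression has no reference value

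*SAP*

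**What the plan says.** All of the endpoint rules below are in SAP Section 9.1.

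- **Bone progression.** Time runs from first study treatment "to first confirmed appearance of at least 2 new bone metastatic lesions".
- **Clinical progression.** Time runs from first study treatment "to date of treatment discontinuation due to disease progression".
- **Censoring for both.** "Patients who are alive and progression-free will be censored at their end of study visit".
- **rPFS, for contrast.** Patients without progression or death "will be right-censored at the time of the last tumor assessment date". DOR follows the same rule, and PSA progression is censored at the last PSA evaluation.
- **PSA progression.** The event is "PSA progression (first occurrence of 50% or greater increase in PSA levels". The text does not say what the increase is measured from, sets no absolute minimum and asks for no confirming value.

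Protocol Section 3.1 limits imaging: "Tumor assessments will be documented until disease progression". Under Protocol Sections 7.5 and 7.5.2, scans continue after treatment only in patients who stopped for a reason other than progression. Survival contact by telephone continues every 4 months until at least 2 years after the last enrolment. Protocol Section 9.5.5 sets censoring rules for rPFS, DOR and overall survival only.

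**The concern.** A patient should stay in the Kaplan-Meier risk set only while the event could be observed. New bone lesions are seen only on a scan. If scans stop because soft-tissue disease progressed and the patient is then followed by telephone, later months carry no information on bone. Likewise, a patient who stops treatment for toxicity can no longer have the clinical-progression event as defined, yet would remain at risk until the end of study. This will occur in practice: under Protocol Section 5.7.1.1, patients who had previously progressed on enzalutamide or a second-generation anti-androgen stop enzalutamide when CORT125281 stops.

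Times to PSA, bone and clinical progression, with the 4-, 6- and 12-month progression-free proportions, are secondary objectives (Protocol Section 2.2, SAP Section 3.2). For bone and clinical progression, the error would make the combination look better than it is. For PSA, two analysts could report different medians from the same data.

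**Working it through.** The documents give no median, event count or rate for these endpoints. There is no plan figure to reproduce, and every rate below is an assumption.

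**Bone, closed form.** Let λb be the hazard of bone progression and λs the hazard of scans stopping for another reason. Assume independent exponential times and no death or administrative censoring before time t. If patients whose scans have stopped stay at risk past t:

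- estimate under the SAP rule: S*(t) = 1 − [λb/(λb+λs)] × [1 − exp(−(λb+λs)t)]
- truth: S(t) = exp(−λb t)

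Take an 8-month median for bone progression, so λb = ln 2/8 = 0.0866, and t = 12 months. The true S(12) is exp(−1.040) = 0.354.

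- Scan-stop median 6 months: λs = 0.1155 and λb+λs = 0.2022. S*(12) = 1 − 0.4286 × (1 − 0.0884) = **0.609**. The curve levels off at 1 − 0.4286 = 0.571, so the median is never reached.
- Scan-stop median 12 months: λs = 0.0578 and λb+λs = 0.1444. S*(12) = 1 − 0.6 × (1 − 0.1768) = **0.506**. The median is ln 6/0.1444 = 12.4 months instead of 8.

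**Bone and clinical, simulation.** This used 200,000 patients per scenario, the protocol's scan schedule (every 8 weeks to week 24, then every 12), a scan when scanning stops, an assumed median of 14 months from that point (or from end of treatment) to death, and administrative end of follow-up at 24 to 36 months. The true median is 9 months in every row.

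| Endpoint | Median time to stopping for another reason | Median, censored at last scan or end of treatment | Median, censored at end of study | 12-month event-free, same order |
|---|---|---|---|---|
| Bone | 4 months | 8.3 | not reached | 0.36 vs 0.69 |
| Bone | 8 months | 9.2 | 19.3 | 0.40 vs 0.58 |
| Bone | 16 months | 11.0 | 13.8 | 0.41 vs 0.51 |
| Clinical | 6 months | 9.0 | not reached | 0.40 vs 0.62 |
| Clinical | 12 months | 9.0 | 13.5 | 0.40 vs 0.52 |
| Clinical | 24 months | 9.0 | 10.5 | 0.40 vs 0.46 |

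Scenarios with true medians of 6 and 12 months (bone) and 6 months (clinical) were also run. Over all of them, the 12-month rate rose by 0.09 to 0.37 (bone) and 0.06 to 0.26 (clinical). In one bone scenario (true median 6, scan-stop median 16) the median did not move (8.3 both ways), although the 12-month rate rose from 0.26 to 0.37.

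**PSA.** Assume baseline 40, nadir 8 and doubling time 3 months. Times after nadir:

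- 50% over nadir: 3 × log2(12/8) = 1.8 months
- 50% over baseline: 3 × log2(60/8) = 8.7 months

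The missing reference alone moves the event by about 7 months in this example. The direction is not fixed. The comparator below is a confirmed 25% rise over nadir, above 1 ng/mL, with 28-day visits, doubling time 6 months and log-scale noise 0.1:

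- Baseline 20 with a 50% fall: comparator 5.5 months, unconfirmed 50% over nadir 6.4, 50% over baseline 12.9.
- Baseline 1.5 with a 90% fall: comparator 20.2 months, unconfirmed 50% over nadir 7.4, which is earlier.

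**The case against.** **The term may mean the end-of-treatment visit.** The scheduled visits are end of treatment, 30 days later, and 4-monthly follow-up; none is an end-of-study visit. The SAP's rule for symptomatic skeletal events joins study and treatment in one label for the 30-day visit, and the amendment log records an end-of-study label being renamed end of treatment. On that reading clinical censoring is appropriate, and the bone gap is usually small because a scan is due at end of treatment unless one was done within 4 weeks. This stands as a reason to call the term undefined, but it does not remove the problem. The overall-survival table in SAP Section 9.1 lists end of study and end of treatment as separate sources, and SAP Section 8.1 tabulates the two discontinuations separately. End of treatment is also not the last bone scan for patients who stay on treatment after progression (Protocol Section 4.4.1) or who are scanned after it.

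**The rule may not cover the key patient.** Someone with soft-tissue progression is arguably no longer progression-free. If so, the SAP has no rule for that patient, and that gap also needs closing.

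**A reader might infer that all three times to progression are overstated.** The documents do not support this for PSA. Its censoring date is right, the reference is missing, and the lack of confirmation and of a minimum can bring events forward. The 80% fall in the worked PSA example is also large: the plan's background rates for even a 50% fall are 23.5% and 8%. With no fall, nadir equals baseline and the choice between them does not matter.

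**A reader might take the protocol's rising-PSA rule as the endpoint definition.** "Rising PSA: 25% increase over nadir and an absolute value of" more than 1 ng/mL, on two measurements, is an eligibility criterion for Segment 2. The protocol does not define PSA progression, and Appendix B gives no PSA-progression criterion.

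**Conclusion.** The point holds for bone and clinical progression. The censoring date is undefined, and if it means end of follow-up it biases both curves upward whenever follow-up outlasts observation of the event. The direction follows from the rule; the size does not. The 51% and 61% against 35% rest on assumed medians, exponential times, independence and no deaths before 12 months, and should be read as illustrations, not predictions for this trial. Independence matters for the remedy too: censoring at the last scan is unbiased only if the reason scans stop is unrelated to bone risk.

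For PSA progression the finding is that the endpoint is not reproducible, with unknown direction of bias.

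This should be fixed, but it is not critical. The endpoints are secondary and descriptive. The DLT/MTD objective, rPFS and the PSA-response sample size are unaffected.

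**What to change.** In SAP Section 9.1:

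1. Censor bone progression at the last adequate bone scan.
2. Censor clinical progression at the last disease evaluation on or before treatment discontinuation for a reason other than progression.
3. For both, state how deaths without progression are handled. For bone, also state how non-bone progression is handled.
4. Remove the end-of-study visit as a censoring date, or define it.
5. Define PSA progression in full: the reference (nadir, or baseline if there is no decline), the absolute minimum, the confirmation rule and the event date. If a PCWG3 criterion is intended, write it out.

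The cost is a few sentences before unblinding. No new data collection is involved. If the term meant end of follow-up, reported times to bone and clinical progression will generally become shorter.

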9.2. Exploratory Efficacy Endpoints

Change from baseline in PSA score: Summary statistics will be provided for PSA score at screening, baseline and at each of the post-baseline time points during the observation period. The changes of PSA score from baseline will be summarized by post-baseline visits. Patient data will be listed. Waterfall plots will be generated for maximum reduction in PSA (%) from baseline, and for best reduction in PSA (%) from any timepoint.

Patient Reported Outcomes (PRO) and Quality of Life (QoL) Assessments: PRO and QoL assessments will be listed and summarized using data from the Safety population.

The FACT-P questionnaire and additional questions to capture patient-reported pain will be used on study.

FACT-P: Patient responses to the 39 items of the instrument will be scored to obtain an overall and four subscale scores with lower scores indicating greater symptom burden. Possible ranges for the calculated scores would be:

- Overall (FACT-P): 0 – 156
- Physical Well-Being (PWB): 0 – 28
- Social/Family Well-Being (SWB): 0 – 28
- Emotional Well-Being (EWB): 0 – 24
- Functional Well-Being (FWB): 0 – 28
- Prostate Cancer Subscale (PCS): 0 – 48

Some items are reverse scored. Reversals will be performed as indicated by FACT-P Scoring Guidelines (Version 4) and individual items will be summed to obtain a score. If there are unanswered items, the total score will be multiplied by the number of items in the subscale and then divided by the number of items answered. This produces the subscale score. A higher score indicates better quality of life (QoL).

Health-related quality of life will be assessed in the Safety population and analysis subgroups (enzalutamide or abiraterone naïve, prior treatment with abiraterone, enzalutamide resistant, ARV7 positive and ARV7 negative, and GR positive and GR negative) using the FACT-P questionnaire at the time points shown in the SoA. Patients who discontinue exicorilant + enzalutamide due to reasons other than disease progression will continue to be assessed until unequivocal progressive disease is documented.

Patient listing for all subscales of FACT-P will be presented by visit and treatment group.

Specific endpoints to characterize the quality of life in patients will include:

- Median time to clinically meaningful deterioration defined as the first occurrence of ≥ 10 -point decrease from baseline on FACT-P score with no subsequent observations with an increase of 10 or more points from baseline.
- Change from baseline to each visit in the overall FACT-P score, as well as its subscales, and pain-related score.
- Percentage of patients who filled out the survey and showed a ≥ 10 -point improvement in FACT-P score, with no subsequent observations with a decrease of 10 or more points from baseline.

The distribution of time to deterioration will be summarized using the Kaplan-Meier method. The score and change from baseline in the FACT-P score and its subscales will be summarized by visit, by arm and overall. The baseline and post-baseline FACT-P score and its subscales will be analyzed using the paired t test for all patients in the ITT population.

Patient-Reported Pain: Additionally, at each study visit, patient-reported worst pain level within past 24 hours and its change from baseline will be summarized by arm and overall.

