6.9 Patient-Reported Outcomes and Quality-of-Life Assessments

The Functional Assessment of Cancer Therapy-Prostate (FACT-P) questionnaire and additional questions to capture patient-reported pain will be used on study.

The FACT-P questionnaire is a validated questionnaire, used worldwide for assessing the health-related QoL in men with prostate cancer. FACT-P consists of FACT-G (general), a 27-item self-report questionnaire that measures general health-related QoL in cancer patients, and a 12-item prostate cancer subscale (PCS). The PCS is designed specifically to measure prostate cancer-specific QoL. Patients' overall physical and emotional well-being, based on subscales of the FACT-G and the PCS, PCS pain-related score, and other prostate cancer-specific QoL components, will be assessed using the questionnaire.

Questions to capture the patients reported pain will be reported in the appropriate eCRFs in addition to the FACT-P questionnaire. Pain is the most established PRO in the mCRPC population and is associated with inferior survival and diminished QoL ([Scher et al. 2016](#)).

The PRO and QoL questionnaires will be completed at the time points shown in the SoA ([Appendix A](#)). The questionnaires should be administered before discussing imaging scan results or disease status changes with the patient. The questionnaires should continue as a study procedure in patients who discontinue study treatment prior to disease progression until unequivocal progressive disease is documented. The questionnaires can be administered by self-report (paper) or interview by qualified site personnel (face-to-face or telephone).

The Sponsor will provide training for relevant personnel (eg, key Investigators, clinical research associates) in the administration of the questionnaires, so that patients fill in the questionnaires as completely and accurately as possible. It is important that the significance and relevance of the data are explained carefully to participating patients so that they are motivated to comply with data collection. The measures are self-reported and the patient must complete the questionnaires in private and should not be given help from relatives or clinic staff; help in interpreting the questions is not allowed.

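### SAP 9.2 prorates FACT-P subscales with no minimum number of answered items, so one sparsely completed subscale can by itself create or hide the 10-point change that defines the endpoints

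*SAP*

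**What the plan says.** SAP 9.2 (Exploratory Efficacy Endpoints) describes FACT-P scoring in three steps. The first covers reversals and summing: "Reversals will be performed as indicated by FACT-P Scoring Guidelines (Version 4) and individual items will be summed to obtain a score". The second covers missing items: "If there are unanswered items, the total score will be multiplied by the number of items in the subscale and then divided by the number" (the divisor is the count answered). The third closes the rule: "This produces the subscale score". No condition is attached to the second or third step.

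No completeness condition appears elsewhere either. SAP 7.4 says only that missing data are not imputed unless specified, and the proration in 9.2 is such a specification. Protocol 6.9 and 9.6 describe the questionnaire and its analyses without a scoring threshold. The Scoring Guidelines appear in the SAP reference list, but the text calls on them only for the reversals.

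The scores feed these analyses in SAP 9.2:

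- Time to deterioration: "Median time to clinically meaningful deterioration defined as the first occurrence of" a fall of at least 10 points from baseline in FACT-P score, with no later observation 10 or more points above baseline.
- The percentage of patients with an improvement of at least 10 points, with no later observation 10 or more points below baseline.
- Change from baseline by visit, and paired t tests.

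**The concern.** Proration assumes that the answered items represent the unanswered ones. That is reasonable when most items are present and weak when one or two are. The rule treats both cases alike: with k of m items answered, each answered point counts m/k times. The deterioration and improvement thresholds do not move with k. A form that is nearly blank in one subscale can therefore register as a clinically meaningful change, or conceal one, on the strength of one or two answers.

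The groups are small. Segment 2 plans 12 and 4 DLT-evaluable patients in Arms A and B, and each expansion cohort plans about 20. Taking those numbers as illustrative denominators, one spurious change of 12 points shifts a mean change by 12/12 = 1.0 point in Arm A, 12/4 = 3.0 in Arm B and 12/20 = 0.6 in an expansion cohort. One false event in Arm B is 1 patient in 4.

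**Working it through.** **Reproducing the plan's scale.** SAP 9.2 gives "Overall (FACT-P): 0 – 156", "Prostate Cancer Subscale (PCS): 0 – 48", and maxima of 28, 28, 24 and 28 for physical (PWB), social/family (SWB), emotional (EWB) and functional (FWB) well-being. The maxima sum to 28 + 28 + 24 + 28 + 48 = 156, as stated. With 39 items, each item carries 156/39 = 4 points. The item counts are therefore 7, 7, 6, 7 and 12, which sum to 39. This agrees with Protocol 6.9 (27 general items plus 12 prostate items).

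**Formula.** Subscale score = (sum of answered items) × m/k, where m is the number of items in the subscale and k the number answered. One raw point moves the subscale, and the total if nothing else moves, by m/k.

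| Subscale | m | k | Points per raw point (m/k) | Raw points needed to reach 10 |
|---|---|---|---|---|
| PCS | 12 | 1 | 12 | 1 (gives 12) |
| PCS | 12 | 2 | 6 | 2 (gives 12) |
| PWB, SWB, FWB | 7 | 1 | 7 | 2 (gives 14) |
| EWB | 6 | 1 | 6 | 2 (gives 12) |
| PCS | 12 | 7 | 1.71 | 6 |
| PCS | 12 | 12 | 1 | 10 |

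**False deterioration from a 1-point change.** Suppose all 39 items are 3 at baseline: 39 × 3 = 117. At follow-up the 27 general items are still 3 (27 × 3 = 81) and only one prostate item is answered.

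- If it is 2: PCS = 2 × 12/1 = 24, total = 81 + 24 = 105, change = −12.
- If it is 1: PCS = 12, total = 93, change = −24.

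**False deterioration with no item changed.** Suppose baseline PCS is 36, made of one item at 2 and eleven items summing to 34. If only the item at 2 is answered later, still at 2, PCS = 2 × 12 = 24. The fall is 12 points, although no answered item differs from baseline.

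**Hidden deterioration.** Start again from 117. If the general items fall from 81 to 69 and the one answered prostate item is 4, PCS = 48 and the total is 69 + 48 = 117. The change is 0, despite a 12-point fall on fully answered items.

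**Persistence.** In the first example the event at 105 is cancelled only if a later score reaches 117 + 10 = 127. A later complete form at 117 leaves it in place.

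**Boundary.** With k = 0 the formula divides by zero. The SAP does not say what the total is when a whole subscale is blank.

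**The case against.** The strongest reply concerns the cited guideline. The SAP names the FACT-P Scoring Guidelines in the sentence just before the proration rule and lists them as a reference. The rule could be a shortened paraphrase of the guideline, with the guideline's conditions still meant to apply. The guideline is not available here, so that cannot be excluded. What stands is narrower: the SAP text states no floor, and a programmer following it would apply none.

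Second, the 1-point result is a corner case. It needs exactly one prostate item answered, and the other subscales must not rise by more than 2 points in compensation (−12 + 2 = −10 still counts; −12 + 3 = −9 does not). With two prostate items answered, one raw point moves the total only 6; in the other subscales with one item answered it moves 6 or 7. A reader might infer that any 1-point change on an incomplete form triggers an event. It does not, although a 2-point change can in the settings tabulated above.

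Third, nothing in the documents says how often forms are this sparse. Protocol 6.9 provides for training in questionnaire administration so that forms are filled in as fully as possible, and it allows interview administration. Both make near-blank subscales less likely, though neither is a scoring rule. A reader might also infer that incomplete forms drive the FACT-P results, or that they cluster near progression. The documents support neither inference, and the finding needs neither.

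Fourth, FACT-P is exploratory in both documents. This stands and limits the weight of the point.

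**Conclusion.** The gap is real. SAP 9.2 states an unconditional proration rule that, applied literally, scores a 12-item subscale from one answer and can move the total by 12 points or more on one or two raw points, or on none. The direction is not fixed: it can create or hide either a deterioration or an improvement. Nothing here shows a net bias.

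The reach is limited to the exploratory FACT-P summaries: time to deterioration, improvement percentage, change from baseline and the paired t tests. The DLT analysis, the recommended-dose decision and the expansion-phase PSA criteria do not use FACT-P, so no inference about those should be drawn.

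The conclusion assumes that the SAP text is followed as written and, for the single-subscale figures, that the other subscales are unchanged. The frequency of affected forms is unknown. The change is worth making because the rule as stated can give a wrong score and the correction is short.

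**What to change.** Add a minimum-completeness condition to SAP 9.2 for prorating a subscale and for computing the total, and set the score to missing at that visit when it is not met. Fix it before unblinding, in line with SAP 1.1, so that it is not chosen after partial forms have been seen. If the cited guideline has such a rule, say expressly that it governs.

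A proposed assumption, not taken from the documents and to be checked against the guideline, is:

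- Subscale: prorate only if more than half of its items are answered, that is at least 4 of 7, 4 of 6 and 7 of 12.
- Total: compute only if all five subscales are scorable and at least 80% of the 39 items are answered (0.8 × 39 = 31.2, so 32). The subscale minima alone would allow 4 + 4 + 4 + 4 + 7 = 23 items, so the second condition adds protection.

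At these floors one raw point moves a subscale by 7/4 = 1.75, 6/4 = 1.5 or 12/7 = 1.71 points, and at least 6 raw points are needed to reach 10. The floor reduces the problem without removing it. For example, with seven prostate items at 2 and five at 4, PCS is 14 + 20 = 34; if only the seven are answered later, unchanged, it is 14 × 12/7 = 24, a fall of 10.

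The cost is a sentence or two in the SAP and some missing visit scores. Setting scores to missing could delay or lose some true deterioration events, so report the number set to missing by visit and arm.
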